**Title: Oxytocin in Cocaine Dependence**

**NCT: 01573273**

**Date of Document: 8/1/2016**

## Oxytocin in Cocaine Dependence

### SPECIFIC AIMS

Previous work conducted by the MUSC SCOR identified sex/gender differences in preclinical and clinical models of cocaine cue and stress reactivity that may contribute to gender differences in relapse. The proposed project will build on this work by exploring potential mechanisms for these sex/gender differences. Specifically, several studies have indicated that hypothalamic neuropeptides mediate behavioral responding to stress as well as play a role in neuroadaptations that occur as a consequence of long-term cocaine use. The hypothalamic neuropeptide oxytocin promotes trust, social bonding, and calmness. Given these effects, oxytocin may have a therapeutic role in ameliorating the negative affect commonly observed prior to relapse in cocaine-dependent individuals. As estrogen appears to enhance oxytocin's effects, women may have an enhanced response to oxytocin. The specific aims of the proposed project are:

**Specific Aim 1: Using a human laboratory paradigm, determine the impact of oxytocin on stress-induced craving in cocaine-dependent women and men.**

Preclinical and clinical investigations have found that the neuropeptide oxytocin exerts anxiolytic effects in stress paradigms. However, little is known about the potential anxiolytic effects of oxytocin in cocaine-dependent individuals, or if a gender differential in response exists.

**Hypothesis 1a:** Intranasal administration of oxytocin will attenuate drug craving response and stress reactivity to a psychosocial stress task in cocaine-dependent individuals compared to placebo administration.

**Hypothesis 1b:** The ameliorative effects of oxytocin on drug craving response and stress reactivity will be more pronounced in cocaine-dependent women as compared to cocaine-dependent men.

**Exploratory Hypothesis 1c:** The stress and craving reduction induced by oxytocin in women will be related to estrogen and progesterone levels.

**Specific Aim 2: Using a neuroimaging cue paradigm, explore the impact of oxytocin on neural correlates and subjective responses of cocaine cue reactivity in cocaine-dependent men and women.**

Presentation of cocaine-paired cues elicits a stress response in cocaine-dependent individuals. Neuroimaging studies indicate substantial overlap in the corticostriatal limbic circuitry responsible for cue and stress-primed drug craving. Oxytocin receptors have been localized to these same regions and preclinical studies have shown that oxytocin attenuates the acute reinforcing properties of psychostimulants. Despite these findings, little is known about the role of oxytocin in modulating the affective response to cocaine-paired cues and associated neural activity in cocaine-dependent men and women and whether there are gender differences in this modulation.

**Hypothesis 2a:** Intranasal administration of oxytocin will decrease subjective ratings of cue-induced cocaine craving in cocaine-dependent men and women compared to placebo administration.

**Hypothesis 2b:** Intranasal administration of oxytocin will decrease functional activity in the anterior cingulate cortex, amygdala, striatum, and prefrontal cortex compared to placebo administration.

**Exploratory Hypothesis 2c:** The attenuation of functional activity in the anterior cingulate cortex, amygdala, striatum and prefrontal cortex following oxytocin administration will be greater in cocaine-dependent women as compared to cocaine-dependent men.

**Exploratory Hypothesis 2d:** Oxytocin will modulate resting-state and task-related functional connectivity among sub-networks implicated in reward and motivation (nucleus accumbens, and orbitofrontal cortex),

memory and learning (amygdala and hippocampus), and cognitive control (prefrontal cortex and anterior cingulate cortex). Oxytocin may increase connectivity between reward/motivation and cognitive control sub-networks in craving states as an index of top-down regulation.

**In summary**, the proposed project will provide important data on the effect of oxytocin on stress and craving in cocaine-dependent individuals, explore the neural circuitry involved in response to oxytocin administration, and investigate whether sex/gender differences in response exist.

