related pictures compared to rest. **Figure 3** shows the modular structure based on the group-averaged correlation matrix. In the rest condition, 4 modules emerged (color coded in **Figure 3**), but in the cocaine condition, there was significant reorganization of the modules relative to rest. The blur condition was identical to rest whereas the object condition was different from both the rest and cocaine conditions. Notably, in the cocaine condition there was greater integration across brain regions as evidenced by the emergence of only 3 modules. In addition, the diversity coefficient (which is a measure of functional integration) was greater in the cocaine than the rest condition for all regions that changed module membership in the cocaine condition (**Figure 3**-cocaine; all  $p$ 's < .05) except for the right middle occipital gyrus (region 52). Regions that became more integrated with the fronto-parietal module (green) included the insula, posterior cingulate, auditory cortex, and dorsal visual regions. We speculate that this reorganization reflects heightened attention to and salience of the cocaine stimuli given the characterization of fronto-parietal cortex as a dorsal attention network (Fox et al., 2006) and insula-cingulate connections as part of a salience network (Menon & Uddin, 2010). There was also increased connectivity/integration of ventral visual regions with temporal and ventro-medial prefrontal regions which may reflect strong engagement of memory systems related to the cocaine images (Childress et al., 1999). Although some typical reward-related regions (caudate, putamen; blue module) were dissociated from the other modules in the cocaine condition, this also occurred when participants were viewing objects. The other changes in module membership in **Figure 4** were specific to the cocaine condition. Although this is a preliminary analysis, it demonstrates the feasibility of conducting graph theory-based functional connectivity analysis for the proposed project. In addition, regions that changed module membership in the cocaine condition included some of the same regions that have oxytocin receptors (e.g., amygdala, anterior/posterior cingulate, and striatum). Finally, [name], a major developer of the BCT, has agreed to be consultant on this project (see Letter of Support). He is currently integrating network-based statistics (Zalesky et al., 2010) into the BCT to allow for group comparisons of functional networks.

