[figure not shown]

**Figure 3.** Results of the modularity partition based on the average correlation matrix among 90 regions in the rest (left) and cocaine (right) conditions of a cue-induced craving fMRI study of 37 cocaine users. Numbers indicate the region as specified in the AAL atlas and size of each node represents its average strength (i.e. sum of positive connections). Modules in the resting state include fronto-parietal (green), ventral-visual/temporal/orbitofrontal (red), dorsal visual (yellow) and basal ganglia/thalamus/auditory/insula (blue) sub-networks. Regions that reorganized when viewing cocaine images are noted by labels in the cocaine condition.

some of the same regions that have oxytocin receptors (e.g., amygdala, anterior/posterior cingulate, and striatum). Finally, [name], a major developer of the BCT, has agreed to be consultant on this project (see Letter of Support). He is currently integrating network-based statistics (Zalesky et al., 2010) into the BCT to allow for group comparisons of functional networks.

**C.1.e. Summary.** As demonstrated by the work above, the research team has experience with stress-induction studies ([name], [name], [name]), cue-reactivity research ([name], [name]), administration of oxytocin ([name]), neuroimaging ([name], [name], [name]), functional connectivity analyses ([name], [name]), and recruitment and retention of cocaine-dependent individuals for participation in laboratory-based studies ([name], [name]). Hence, the study team has the necessary skills to ensure the successful completion of the proposed study.

**C.2. Research Design and Methods.** In this project, the impact of acute pre-treatment with oxytocin (40 IU) or placebo on the subjective and physiologic response to the Trier Social Stress Task (TSST) in men and women with cocaine-dependence will be investigated. Additionally, participants will complete two functional magnetic resonance imaging (fMRI) scans in the presence of cocaine-related cues. Prior to each scan, participants will receive either oxytocin (OXY) or placebo (PBO) in a counter-balanced, double-blind fashion. A schematic of study procedures is shown below.

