For Exploratory Hypothesis 2d, a graph-theory approach to functional connectivity will be used. The BCT (Rubinov & [name], 2011) includes metrics specifically designed for functional brain networks, which are fully connected with weighted and signed connections. The metrics combine both positive and negative weights, but weight the positive connections more heavily. Within each of 116 anatomical regions of the AAL atlas, the average intensity value at each time point will be extracted for each subject. The time series (shifted by one TR) will be segmented into four separate time series, one for each condition (cocaine images, blur, objects, rest) (Fair et al., 2007; Just et al., 2004). Correlation matrices will then be computed for each subject and each condition and submitted to the BCT. For each subject and each condition, several BCT metrics will be computed (see Rubinov & [name], 2011 for more details). Network measures include *modularity* and *number of modules*. Node-specific measures include *diversity coefficient*, *within-module weights*, *within-module clustering coefficient*, and *strength*. We will also compute 20 random networks for each subject that preserve the weight and strength properties of the cocaine network (following Rubinov & [name], 2011), since that is the network of most interest. The same metrics that are computed for the cocaine, object, blur, and rest networks will be computed for the 20 random networks, then averaged to provide a single metric for the random network. In addition, a group-average correlation matrix will be computed (Pearson r-values from individual participants are Fisher z-transformed prior to averaging) for each of the four conditions and subject groups to obtain a modularity partition for the group, which will be visualized using Gephi software (Bastian, Heymann, & Jacomy, 2009), as in Figure 4. Network and node-based metrics will be submitted to mixed ANOVAs (one ANOVA for each metric and each node in the case of node-based metrics) with gender and treatment as between-subjects variables and condition (cocaine, object, blur, rest, random) as the repeated factor. Most metrics allow for comparison with the random networks except for strength and weight metrics because those are preserved in random networks and will be identical to the cocaine condition.

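### Three of the four node metrics for Exploratory Hypothesis 2d rest on modules that the plan does not hold fixed, so they can move with the module boundaries and can show the predicted effect with the wrong sign

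*Combined protocol and SAP*

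**What the plan says.** Exploratory Hypothesis 2d (Specific Aims) names three sub-networks by region: reward and motivation, memory and learning, and cognitive control. The first appears as "functional connectivity among sub-networks implicated in reward and motivation (nucleus accumbens, and orbitofrontal cortex"; the others are "memory and learning (amygdala and hippocampus), and cognitive control (prefrontal cortex and anterior cingulate cortex". It gives one direction: "Oxytocin may increase connectivity between reward/motivation and cognitive control sub-networks in craving states as an index of top-down regulation".

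The analysis is in C.2.d, Statistical Methods. Mean signals from 116 AAL regions are correlated within each task condition. Then "For each subject and each condition, several BCT metrics will be computed". The network measures are modularity and the number of modules. The node measures are diversity coefficient, within-module weights, within-module clustering coefficient and strength. A group-average matrix is added for each condition and subject group. It yields a group partition whose stated use is visualisation. Testing is by mixed ANOVA: "one ANOVA for each metric and each node in the case of node-based metrics".

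C.2.d does not say which partition the module-based node metrics use. It gives no list of atlas regions for the three sub-networks and no measure of connectivity between them.

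The team's pilot (C.1.d) found four modules at rest, and "in the cocaine condition there was greater integration across brain regions as evidenced by the emergence of only 3 modules".

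**The concern.** A within-module weight, a within-module clustering coefficient and a diversity coefficient have no value until every region has been given a module label. If the labels come from the same data, each quantity has two sources of change: the node's own correlations, and the set of regions counted as its module. The hypothesis is about the first, between sub-networks fixed in advance. The planned ANOVAs cannot separate the two.

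This matters most in the direction that 2d predicts. Two sub-networks that become more connected are the ones a modularity algorithm is most likely to join. Once they are joined, connectivity between them is counted as connectivity within a module. Of the 4 × 116 + 2 = 466 ANOVAs implied by C.2.d (four node metrics on 116 nodes, plus two network measures), 3 × 116 = 348 use a module-based metric. An unstated partition also leaves a choice that could be made after the results are seen.

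**Working it through.** The plan gives no figure to reproduce here; the check is of how the metrics behave.

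**Inputs from the documents.** 116 regions (C.2.d), so 116 × 115 / 2 = 6,670 pairs. Six epochs with one 24 s block per condition and TR 2.5 s (C.2.c.2), so 6 × 24 / 2.5 = 57.6 volumes per condition. The standard error of one Fisher-z correlation is about 1/√(57 − 3) = 0.136, ignoring autocorrelation.

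**Assumptions.** Four modules of 29 nodes, as in the pilot at rest. Metric definitions are standard forms, because C.2.d gives them only by citation. Strength S is the sum of positive weights. Within-module weight W is the sum of weights to the node's own module. Diversity D is −Σ p ln p / ln(m), with p the share of S going to each of m modules. Clustering is the mean cube-root triangle weight inside the module.

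**1. Starting network.** Weights are 0.5 within and 0.1 between modules.
- W = 28 × 0.5 = 14.0
- Each other module contributes 29 × 0.1 = 2.9
- S = 14.0 + 3 × 2.9 = 22.7
- Shares 0.617, 0.128, 0.128, 0.128 give D = 0.784
- Clustering = 0.50

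**2. Boundaries move; the node's own row of correlations is held constant.** Correlations among other nodes are raised until Louvain modularity returns three modules.

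| Case | S | W | D | Clustering |
|---|---|---|---|---|
| Start | 22.7 | 14.0 | 0.784 | 0.50 |
| Two other modules merge | 22.7 | 14.0 | 0.828 | 0.50 |
| Own module merges with another | 22.7 | 14.0 + 2.9 = 16.9 | 0.678 | 0.31 |
| Own-module merger, starting partition kept | 22.7 | 14.0 | 0.784 | 0.50 |

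Diversity goes up or down according to which boundary moved. Strength does not move, and with the partition fixed nothing moves.

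**3. The predicted effect.** Raise the correlations between two modules by 0.10, from 0.1 to 0.2. The node now sends 29 × 0.2 = 5.8 to the other module, and S = 14.0 + 5.8 + 2.9 + 2.9 = 25.6.
- Fixed partition: W stays at 14.0. Shares 0.547, 0.227, 0.113, 0.113 give D = 1.160 / ln 4 = 0.837, up from 0.784.
- If the two modules merge: W = 14.0 + 5.8 = 19.8. Shares 0.773, 0.113, 0.113 give D = 0.692 / ln 3 = 0.630, down from 0.784.

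Whether a merger occurs depends on noise, so this was simulated with 116 nodes, 58 volumes and four settings with assumed correlations of 0.35–0.50 within and 0.10–0.20 between modules. Only the connectivity between two modules was raised, by 0.10. With a fixed partition, diversity rose and within-module weight was essentially unchanged. With re-estimation, within-module weight rose in all four settings and the diversity effect was negative in three.

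**4. Noise with no effect.** The same true network was used twice, with 57 volumes each and 25 simulated subjects. Re-estimation found fewer than four modules in 4, 6 and 5 of 50 partitions (8–12%).

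| Assumed r within / between | SD of change in W, re-estimated / fixed | Ratio | Ratio for D |
|---|---|---|---|
| 0.50 / 0.10 | 3.42 / 2.51 | 1.36 | 0.1826 / 0.1781 = 1.03 |
| 0.40 / 0.20 | 3.78 / 2.65 | 1.43 | 0.0842 / 0.0654 = 1.29 |
| 0.35 / 0.20 | 3.46 / 2.40 | 1.44 | 0.0623 / 0.0526 = 1.18 |

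Further runs at 116 nodes, over within-module r of 0.30–0.50 and between-module r of 0.10–0.25, gave ratios for W from 1.0 to 1.76. The ratio is near 1.0 when the modules are separated well enough to be recovered almost every time.

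**The case against.** The strongest reply is that module reorganisation is what the team wants to measure. C.1.d presents changed membership and higher diversity under cocaine cues as its result, and a merger can be a real change in the network. That stands. It is why re-estimated modules should be kept, but it does not make them a test of sub-networks named in advance.

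Second, re-estimation for each subject is inferred, not stated. The inference is strong, because the number of modules is computed for each subject and condition. If the group partitions were used instead, they too are formed separately by condition and subject group, so the boundaries could still differ across the levels compared.

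Third, 2d is exploratory, and the simulations assume no true session-to-session variation, which would pull the noise ratios towards 1. They also describe the paired session difference, whereas C.2.d enters treatment as a between-subjects factor. Both limits stand, and they concern the noise figure, not the sign reversal.

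Stronger readings are tempting and should be resisted:
- That every planned node metric is affected. Strength uses no module labels.
- That values can shift through a real change with no correlation changing anywhere. Short of the algorithm varying on re-running, a merger needs other nodes' correlations to change; only the given node's own correlations can stay constant.
- That the pilot shows boundaries moving between drug sessions. Its change from four modules to three is between task conditions, in group-averaged matrices, and the blur condition matched rest.
- That the pilot contradicts the pairing of nucleus accumbens with orbitofrontal cortex. Its legend lists "ventral-visual/temporal/orbitofrontal (red), dorsal visual (yellow) and basal ganglia/thalamus/auditory/insula (blue) sub-networks", but never places the accumbens in a module.

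**Conclusion.** The point holds for three of the four node metrics. The plan fixes no partition for them, and either reading of C.2.d lets module boundaries differ across the conditions compared. The main consequence is interpretive: the effect that 2d predicts can appear as higher within-module weight and lower diversity, where a fixed partition shows diversity rising. The sign reversal was found in three of four simulated settings. It rests on four equal modules, about 58 volumes, a 0.10 rise in correlation and standard metric definitions.

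The loss of precision is secondary and uncertain: an SD ratio of about 1.0 to 1.8 for within-module weight at 116 nodes. A reader might infer a several-fold sample-size penalty, but the documents do not give the correlations needed to support one. Nor is the graph analysis invalid as a description of reorganisation. The change is worth making, although 2d is exploratory, because it decides whether the results can be read against the hypothesis.

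**What to change.** In C.2.d:

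1. List the AAL regions that make up each of the three sub-networks in 2d.
2. Define one partition in advance, identical for both drug sessions and all task conditions. It should contain those sub-networks, with the remaining regions assigned from a single group partition pooled over sessions and conditions.
3. Compute diversity, within-module weights and within-module clustering on that partition for the 2d analysis. Strength needs no change.
4. Read the reward-control prediction from connectivity between the two fixed sub-networks, for example the mean Fisher-z correlation over their region pairs.
5. Keep re-estimated partitions for modularity, number of modules, the comparison with random networks, and a sensitivity analysis of the three node metrics.

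The cost is SAP wording and analysis code, with no new data. The downside is small: the main node metrics no longer reflect individual module reorganisation, which the sensitivity analysis retains.

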## RESEARCH STRATEGY

### A. Significance

**Gender differences in cocaine use disorders.** A growing body of literature indicates important gender differences in the symptomatology, course, and treatment of addictive disorders, including cocaine dependence. Approximately 38% of the 5.3 million individuals in the United States who reported cocaine use in 2008 were women (SAMSHA, 2009); despite this lower prevalence of use, there is evidence that women may actually have an increased vulnerability to the development and deleterious consequences of cocaine dependence. Women meet criteria for drug dependence more quickly and enter treatment programs earlier as compared to men (Brecht et al., 2004; Cotto et al., 2010; Hernandez-Avila et al., 2004; McCance-Katz, 1999; Ridenour et al., 2005; Westermeyer & Boedicker, 2000). Cocaine-dependent women also have greater psychiatric, medical, social/family, and employment problems ([name] & Randall, 1999; Elman et al., 2001; Najavits & Lester, 2008; Wong et al., 2002) and are more likely to attribute relapse to negative emotional states and interpersonal conflict than men (Connors et al., 1998; Terry-McElrath et al., 2009). These findings suggest gender differences in cocaine use and dependence which may have important treatment implications.

**Stress and substance use.** Multiple theories of addiction postulate that stress plays an important role in vulnerability and motivation to use and abuse substances ([name] & Sinha, 2005; Higgins & Marlatt, 1975; Koob & Le Moal, 2001; Russell & Mehrabian, 1975). Generally, these models suggest that drug use may begin as an attempt to modulate tension or distress in some cases. Over time, dependence can develop, and motivation for drug use may include treatment of withdrawal symptoms and response to conditioned cues as well as stress relief and mood enhancement. Thus, vulnerability to drug dependence and relapse may be a result of negative reinforcement/relief from stress or positive reinforcement/mood enhancement. Consistent with this model, clinical studies have shown drug or alcohol consumption to be positively associated with subjective reports of stress, lack of support, and avoidance coping (Cronkite & Moos, 1984; Hall, Havassy, & Wasserman, 1991; McMahon, 2001; Pohorecky, 1991). Data from our previous SCOR work also suggests that cocaine use can be related to stress and negative life events (Waldrop et al., 2007a; Waldrop et al., 2007b).

**Stress and craving.** Considerable empirical literature exists demonstrating that internal mood states related to stress and negative emotion can elicit craving in a laboratory setting, even in the absence of drug cues (Childress et al., 1994; Cooney et al., 1997; [name] et al., 2011; Sinha et al., 1999). In cocaine-dependent individuals, studies show that personalized imagery of stress situations as well as exposure to drug-related cues produce significant increases in cocaine craving, heart rate, cortisol, and subjective anxiety (Fox et al., 2008; Sinha et al., 1999; Sinha et al., 2000). Of note, our SCOR data suggests that there may be important gender differences in subjective ratings of stress and craving in response to cocaine cues and interpersonal stressors. Following presentation of cocaine-related cues, peak subjective ratings of stress and craving were correlated in both cocaine-dependent men and women. In response to a social stressor, subjective ratings of peak stress and craving were correlated in cocaine-dependent women; however, a significant correlation was not present in cocaine-dependent men (Waldrop et al., 2010). These findings suggest that stress related to interpersonal triggers is more highly associated with drug craving in women as compared to men. Importantly, several studies have found stress/mood-elicited craving predicted relapse to substance use (Cooney et al., 1997; Killen & Fortmann, 1997; Sinha et al., 2006). We have also recently reported that subjective stress and craving response to a pharmacological stressor (corticotrophin releasing hormone) predicts relapse to cocaine use (Back et al., 2010). Thus, it appears that provocation of subjective

stress not only elicits craving, but it may also independently predict relapse, supporting the targeting of stress-activated pathways for relapse medication development (Winhusen & Somoza, 2001).

**Stress and cue reactivity.** Cue-reactivity paradigms are commonly used in systematic investigations of craving (Drummond et al., 1990). The presentation of cocaine-related cues may also induce stress responses. Data from the previous funding period demonstrated increased subjective feelings of stress in cocaine-dependent individuals following cue presentation (Waldrop et al., 2010). This is congruent with other reports of increased anxiety and negative emotion following cocaine-cue exposure (Fox et al., 2008; Sinha et al., 2000). Further, cocaine-cue videos produced significantly greater brain activity in cocaine-dependent individuals than healthy controls in regions that were activated in response to sad videos. Thus, drug-paired cues may recruit brain regions responsible for the processing of negative affective stimuli (Wexler et al., 2001).

**Oxytocin and stress.** Oxytocin is a nine amino acid neuropeptide with peripheral endocrine and central neural actions that is synthesized in the paraventricular and supraoptic nuclei of the hypothalamus. Peripherally, oxytocin elicits physiologic events necessary for copulation, parturition, and lactation (Ludwig & Leng, 2006). Central release of oxytocin within limbic nuclei has been implicated in “pro-social” behaviors and may also have anxiolytic effects. For example, several preclinical studies have shown that oxytocin increases approach behavior in rats (Witt et al., 1992), and is essential for partner preferences and monogamous pair bonding in prairie voles (Williams et al., 1994). Central administration of oxytocin receptor antagonists prevents pair bonding in female prairie voles without any significant impact on mating. In fact, neonatal nurturing promotes long-term plasticity within the limbic circuitry, while childhood maltreatment has been associated with low urinary oxytocin levels (Francis et al., 2002; Fries et al., 2005). Intranasal administration of oxytocin attenuates anticipatory anxiety, subjective stress, and hypothalamic-pituitary-adrenal (HPA) axis activation to a psychosocial laboratory stress task and increases trust (de Oliveira et al., 2011; Heinrichs et al., 2003; Kosfeld et al., 2005). In addition, intranasal oxytocin attenuates circulating cortisol levels in men with a history of childhood maltreatment (Meinlschmidt & Heim, 2007). In agreement, neuroimaging studies demonstrate that intranasal administration of oxytocin attenuates amygdala activation following stressful and fearful stimuli (Baumgartner et al., 2008; Domes et al., 2007; Kirsch et al., 2005). Taken together, these studies demonstrate that oxytocin may play a potential therapeutic role in ameliorating stress and anxiety.

**Oxytocin and substance use disorders.** Both preclinical and clinical studies suggest that oxytocin may attenuate the effects of both acute and long-term drug use. Molecular studies have localized oxytocin receptors to the mesolimbic dopamine reward circuit, including the amygdala, nucleus accumbens, and ventral tegmental area (VTA) (Vaccari et al., 1998). Similar to drugs of abuse, oxytocin infusion directly into the VTA promotes dopamine release in the nucleus accumbens (Melis et al., 2007). Systemic administration of oxytocin promotes conditioned place preference in rodents, indicating that oxytocin is rewarding (Liberzon et al., 1997). Behavioral studies utilizing animal models of drug reinforcement demonstrate that oxytocin dose-dependently decreases cocaine-induced hyperactivity and stereotypy (Sarnyai et al., 1991; Sarnyai et al., 1992). Interestingly, chronic administration of oxytocin reduces dopamine release in the nucleus accumbens, indicating that oxytocin may be involved in the plasticity that occurs within the reward circuit as a function of repeated drug use (Kovacs et al., 1998). In addition, oxytocin inhibits the development of tolerance to repeated cocaine administration (Sarnyai et al., 1992) and may also attenuate self-administration of cocaine (Sarnyai & Kovacs, 1994). Oxytocin administration has been shown to block methamphetamine-induced locomotor activity and reduce methamphetamine reinstatement (Carson et al., 2010). These preclinical findings implicate oxytocin in the acute effects of stimulants, as well as the long term behavioral consequences of repeated use.

Limited clinical research has examined the effects of oxytocin in drug-dependent populations. Immunohistochemical analysis of post-mortem brains from alcoholics indicate a significant reduction in oxytocin immunoreactivity in the hypothalamus (Sivukhina et al., 2006). Further, mothers using cocaine during pregnancy exhibit significantly lower plasma oxytocin levels, as well as greater hostility and depression as compared to control mothers (Light et al., 2004). Based on a positive preclinical study in which increasing oxytocin levels were hypothesized to moderate the effects of lithium-attenuated cannabinoid withdrawal in rats

(Cui et al., 2001), a trial of lithium on marijuana withdrawal symptoms demonstrated positive outcomes, including decreased anxiety, lending support to this hypothesis (Winstock et al., 2009). These clinical findings, coupled with preclinical reports, *suggest that oxytocin may decrease some symptoms associated with drug dependence such as negative affect, withdrawal, and tolerance*. Our group has recently completed a pilot investigation of oxytocin administration prior to a social stressor task in marijuana-dependent participants. Oxytocin-treated individuals, as compared to placebo, demonstrated a significant trend towards reduced craving and cortisol response (see Preliminary Data). *The proposed study will be the first controlled examination of the effect of oxytocin on stress or cue-induced craving in cocaine-dependent individuals.*

**Neural correlates of drug craving, sex differences, and potential role of oxytocin.** Compulsive drug-seeking in response to stress and drug cues may be a function of disruption in the circuitry responsible for maintaining executive control and response inhibition in response to emotional evocative stimuli (Baler & Volkow, 2006). In support, neuroimaging studies of cocaine-dependent individuals have implicated prefrontal, limbic and striatal regions in both cue and stress-primed drug craving. For example, cocaine cues (videos and guided imagery) increase activity in limbic regions including the amygdala and anterior cingulate cortex of cocaine-dependent individuals but not healthy controls (Childress et al., 1999; Wexler et al., 2001; Garavan et al., 2000). Kilts and colleagues found that activity in the ventral striatum of cocaine-dependent men was significantly greater during cocaine-cue exposure than during exposure to neutral cues (Kilts, et al., 2001). In contrast, stress attenuated activity in frontal, limbic/paralimbic regions and increased activity in the dorsal striatum of cocaine-dependent individuals (Sinha et al., 2005).

Significant sexual dimorphism in frontal-limbic-striatal structure, function, and neurochemistry are well documented (Cahill, 2006). Therefore, it is not surprising that there are sex differences in the neural correlates of drug craving. For example, stressful imagery produced greater activity in the left anterior and right posterior cingulate, left insula, and inferior medial cortices of cocaine-dependent women as compared to cocaine-dependent men (Li et al., 2005). On the other hand, cocaine-dependent women exposed to guided imagery of cocaine use exhibited significantly less activity in the amygdala, insula, orbitofrontal and ventral cingulate cortices as compared to cocaine-dependent men (Kilts et al., 2004).

Interestingly, oxytocin receptors appear to be widely distributed within frontal-striatal-limbic regions. *In situ* hybridization studies have localized oxytocin receptor mRNA in the hypothalamus, rostral regions of the frontal cortex, bed nucleus of the stria terminalis, anterior cingulate, dorsal striatum, and the amygdala (Yoshimura et al., 1996; Yoshimura et al., 1993). In addition, oxytocin administration attenuates amygdala activity to emotional evocative faces (Domes et al., 2007). Of note, the reduction in amygdala activity was observed in response to both aversive and happy faces, indicating that oxytocin may attenuate reactivity to both aversive and appetitive stimuli.

**Functional Connectivity in Cocaine Users.** Measures of resting state functional connectivity have been employed in neuroimaging studies to evaluate the strength of communication within networks encoding functions ranging from vision and somatosensory perception to motivation and executive function (Fox & Raichle, 2007; Fox et al., 2005). Recently, measures of resting state functional connectivity have been applied to substance-dependent populations. The strength of connectivity within regions in the reward circuit was compared between healthy controls and cocaine users. Greater functional connectivity was found between the ventral striatum and orbitofrontal cortex of the cocaine group compared to healthy controls (Wilcox et al., 2011). In contrast, Gu and colleagues found that the strength of connectivity between the ventral tegmental area, thalamus/lentiform nucleus/ventral striatum, medial prefrontal cortex, and amygdala was significantly lower in cocaine-dependent individuals as compared to controls (Gu et al., 2010). Tomasi and colleagues found that cocaine abusers exhibited significantly lower connectivity between the midbrain, thalamus, rostral cingulate cortex, and cerebellum (Tomasi et al., 2010). This disparity in findings indicates the need for additional studies assessing functional connectivity in cocaine-dependent individuals. Moreover, the strength of functional connectivity during exposure to cocaine cues has not been explored.

**Impact of estrogen and progesterone on reward, craving, and response to oxytocin.** Estrogen and progesterone levels fluctuate throughout the menstrual cycle. Progesterone levels peak seven to twelve days after ovulation marking the middle of the luteal phase; estrogen levels dominate throughout the cycle but peak six to ten days after the start of the menstrual cycle, marking the mid-follicular phase (Evans et al., 2002). In addition to sex differences in brain structure, function, and neurochemistry, circulating gonadal hormones play a critical role in mediating the subjective response to the drug itself, cues, and stress. Preclinical studies have localized estrogen and progesterone receptors to brain regions responsible for mediating the physiological and behavioral response to stress and cues (Alves et al., 1998; Cushing & Kramer, 2005; Laflamme et al., 1998). Preclinical studies conducted by MUSC SCOR investigators demonstrated that cocaine seeking is significantly attenuated during the proestrus phase of the estrous cycle when progesterone levels are highest (Feltenstein & See, 2007; Kippin et al., 2005). In a recent study of treatment-seeking cocaine-dependent women, subjective craving following exposure to a laboratory stressor was significantly lower in women with elevated progesterone compared to women with low progesterone (Sinha, et al., 2007). It has also been demonstrated that ovarian hormone levels can impact the response to smoked cocaine with the positive or “rewarding” effects of cocaine significantly lower during the luteal phase compared to the follicular phase (Evans et al., 2002; Sofuoglu et al., 1999). Taken together, these studies indicate that during the follicular phase when estrogen levels are elevated, the positive and rewarding properties of stimulants peak, while increases in progesterone during the luteal phase may decrease craving and/or drug effect.

Surprisingly few studies have examined the impact of ovarian hormones on the neural correlates of drug craving; however; neuroimaging studies of healthy women tested at different phases of their menstrual cycle are intriguing. For example, Goldstein and colleagues compared brain activity of healthy women exposed to images depicting negative affective stimuli during both the early and late follicular/mid-cycle phase of their menstrual cycle. Activity within the limbic regions was significantly greater during early as compared to late follicular phase (Goldstein et al., 2005). In addition, during the late follicular phase, the magnitude of activity in the amygdala was correlated with arousal, a pattern not observed early in the cycle when both progesterone and estrogen are low. While these data suggest that estrogen may attenuate limbic reactivity to emotional evocative stimuli in healthy subjects, the role of progesterone is unclear since subjects were not tested during the luteal phase of their cycle. Dreher and colleagues measured the limbic response to uncertain anticipated monetary reward in healthy women during the mid-follicular and mid-luteal phases of their menstrual cycle. Anticipation of uncertain rewards produced significantly greater activity in the amygdala and orbitofrontal cortex during the follicular phase than the luteal phase of their cycle (Dreher et al., 2007), suggesting that estrogen may enhance limbic responding to predictors of reward.

